#### 5.5.3.2 Concomitant Influenza Vaccination Analysis

To account for the possibility that the stroke outcome is occurring due to influenza vaccination or due to a combined effect between influenza and bivalent booster vaccination, a subgroup analysis will be conducted to assess stroke risk among beneficiaries with:

- I. Same day vaccination of a COVID-19 bivalent booster and a high dose or adjuvanted influenza vaccine
- II. A COVID-19 bivalent booster without any concomitant influenza vaccination (high-dose, adjuvanted, recombinant, or standard-dose). Concomitant vaccination defined as the receipt of a bivalent booster and a high-dose or adjuvanted influenza vaccine on the same day.

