### 2.1 Primary Objectives

The primary objectives of this study are to evaluate:

- I. The risk of stroke outcomes (as defined in Section 4.3) following exposure to the Pfizer-BioNTech COVID-19 Vaccine, Bivalent and Moderna COVID-19 Vaccine, Bivalent booster doses (by brand) among Medicare beneficiaries age 65+.
- II. The risk of stroke outcomes following exposure to the Pfizer-BioNTech COVID-19 Vaccine, Bivalent and Moderna COVID-19 Vaccine, Bivalent booster doses (by brand) among age groups, those with a prior COVID-19 infection, and those who received a concomitant (same day administration) high-dose or adjuvanted influenza vaccine (see Section 5.5.3 for subgroup definitions).

The analysis for the primary objectives compares the risk of each outcome in a time interval after vaccination (risk window) to that in time intervals post-vaccination after completion of the risk window (control window) within the observation period.

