### 5.3.2 Secondary Analysis II: Influenza Vaccines

Eligible vaccinated individuals for the secondary analysis – influenza vaccination are persons who received a high-dose or adjuvanted influenza vaccine, and who did not receive a same day concomitant bivalent booster. All eligible vaccinated individuals will be used for the attributable risk (AR) calculation.

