### 5.4.1 Observation Period/Follow-Up

For each individual, the observation period will start from the day following bivalent booster vaccination date, i.e., day 1 after vaccination and until the earlier of 90 days post-vaccination, disenrollment, administration of a subsequent mRNA COVID-19 vaccine, death or study period end. Day 0 (date of vaccination) is not included in the observation period since we would not be able to attribute stroke outcomes on this day to the exposure.

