**Table 6. Descriptive Statistics**

Covariates	Data Sources
Age (Categorical)	Medicare Enrollment Database

Covariates	Data Sources
Sex CMS Medicare Race/Ethnicity HHS Region Urban/Rural Status Dual Eligibility Facility/Provider Type Reason for Entering Medicare	Medicare Enrollment Database Medicare Enrollment Database Medicare Enrollment Database Medicare Enrollment Database Medicare Enrollment Database Medicare Enrollment Database Medicare Enrollment Database
Outcome Setting  IP  OP-ED	Medicare Claims  Medicare Claims
Concomitant Influenza Vaccination – Same Day as Bivalent Booster Administration High-dose  Adjuvanted  Recombinant  Live-attenuated  Cell-cultured  Standard	Medicare Claims  Medicare Claims  Medicare Claims  Medicare Claims  Medicare Claims  Medicare Claims
Other Vaccinations – Administered During Risk/Control Intervals Pneumococcal	Medicare Claims
Prior COVID-19 diagnosis (relative to outcome date)  COVID-19 diagnosis in the 30 days prior  COVID-19 diagnosis in the 31 to 365 days prior	Medicare Claims  Medicare Claims
Presence of Medical Conditions Hospitalization (prior 12 months) Ischemic Heart Disease Hypercholesterolemia Hypothyroidism Chronic Kidney Disease Heart Failure Chronic Obstructive Pulmonary Disease Asthma Gout Obesity	Medicare Claims Medicare Claims Medicare Claims Medicare Claims Medicare Claims Medicare Claims Medicare Claims Medicare Claims Medicare Claims Medicare Claims

Covariates	Data Sources
Nicotine Dependency ITP Impaired Mobility Depression Charlson Comorbidities Index	Medicare Claims Medicare Claims Medicare Claims Medicare Claims
Nursing Home Measures (For Nursing Home Residents Follow-Up Analysis) Health Inspection Five-Star Rating Health Inspection - 1 Star Health Inspection - 2 Stars Health Inspection - 3 Stars Health Inspection - 4 Stars Health Inspection - 5 Stars	Nursing Home Compare Dataset Nursing Home Compare Dataset Nursing Home Compare Dataset Nursing Home Compare Dataset Nursing Home Compare Dataset
Quality Measure Five-Star Rating Quality Measure - 1 Star Quality Measure - 2 Stars Quality Measure - 3 Stars Quality Measure - 4 Stars Quality Measure - 5 Stars	Nursing Home Compare Dataset Nursing Home Compare Dataset Nursing Home Compare Dataset Nursing Home Compare Dataset Nursing Home Compare Dataset

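### Section 5.5.3.2 defines the bivalent-without-influenza group in two conflicting ways, and neither it nor Secondary Analysis II fully covers the other vaccine given on a nearby day

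*Protocol*

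**What the plan says.** Section 5.5.3.2 gives the purpose of the subgroup: "To account for the possibility that the stroke outcome is occurring due to influenza vaccination or due to a combined effect" of the two vaccines. Group I is same-day receipt of the booster and a high-dose or adjuvanted influenza vaccine. Group II is "A COVID-19 bivalent booster without any concomitant influenza vaccination (high-dose, adjuvanted, recombinant, or standard-dose"). The sentence that follows reads: "Concomitant vaccination defined as the receipt of a bivalent booster and a high-dose or adjuvanted influenza vaccine on the same day".

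Table 6 tabulates six influenza vaccine types under "Concomitant Influenza Vaccination – Same Day as Bivalent Booster Administration", adding live-attenuated and cell-cultured to the types named in item II. Under "Other Vaccinations – Administered During Risk/Control Intervals" it lists only pneumococcal vaccine.

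Follow-up in the bivalent analysis (Section 5.4.1) runs "until the earlier of 90 days post-vaccination, disenrollment, administration of a subsequent mRNA COVID-19 vaccine, death or study period end". Influenza vaccination is not on that list. It is not among the exclusions in Section 5.3.1 either, and the model in Section 5.5.2.1 has only the two risk-window terms for the booster.

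Secondary Analysis II, which Section 2.2 describes as estimating the independent influenza vaccine risk, takes influenza vaccine recipients "who did not receive a same day concomitant bivalent booster" (Section 5.3.2). Section 5.4.1.1 also ends follow-up at a further influenza vaccine or any mRNA COVID-19 vaccine.

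**The concern.** Group II is meant to show the booster's risk free of influenza vaccine, and Secondary Analysis II is meant to show the reverse. Two things work against this.

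First, the membership rule for group II can be programmed in two ways, giving different groups.

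Second, the other vaccine can be given on a day other than day 0, and its risk period can then fall in the risk or control time of the index vaccine. In group II this can happen with an influenza dose before or after the booster. In Secondary Analysis II it can happen with a booster given before the influenza dose. An excess belonging to one vaccine would then be partly credited to the other. If it fell in control time, it would pull the estimate down. Table 6 would not show how often this occurs, because influenza vaccination on other days is not tabulated.

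**Working it through.** The protocol gives no figure on this point, so there is nothing to reproduce. The check compares the rules and then illustrates the size.

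**Who is in group II?**

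| Same-day influenza vaccine | Item II | Next sentence |
|---|---|---|
| High-dose or adjuvanted | out | out |
| Recombinant or standard-dose | out | in |
| Live-attenuated or cell-cultured | not listed | in |

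**Which rule covers the other vaccine on another day?**

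| Timing | Bivalent analysis (5.3.1, 5.4.1, 5.4.3, 5.5.2.1) | Influenza analysis (5.3.2, 5.4.1.1) |
|---|---|---|
| Before the index dose | none | none |
| After the index dose | none | follow-up ends at any mRNA COVID-19 vaccine |

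The three-day rule in Sections 4.2 and 5.3.1 does not fill the gap. It also removes people given several brands on the same day. If it reached across vaccine types it would empty group I, so it must apply within one type. The seasonality analysis in 5.5.4.1 specifies a baseline-rate offset from earlier years, not individual influenza doses.

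**Size, under assumptions.**

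- From the protocol: risk windows of days 1-21 and 22-42, and control days 43-90 (48 days).
- Assumed: true index IRR of 1; a share p of the group had the other vaccine on day d relative to the index dose; that vaccine multiplies the rate by r on its own days 1-21; full 90-day follow-up.

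If k days of a window of length L are affected, the mean relative rate there is m = 1 + (r − 1)k/L. The apparent IRR is [(1 − p) + p·m_risk] / [(1 − p) + p·m_control], which simplifies to [1 + p(r − 1)k_risk/21] / [1 + p(r − 1)k_control/48].

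With p = 0.3 and r = 1.5, p(r − 1) = 0.15. For days 1-21:

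- Doses 1 day apart: 20 of 21 days affected, 1 + 0.15 × 20/21 = 1.14.
- Doses 7 days apart: 14 of 21 days, 1 + 0.15 × 14/21 = 1.10.
- Doses 14 days apart: 7 of 21 days, 1 + 0.15 × 7/21 = 1.05.
- Other vaccine 20 days before: 1 of 21 days, 1 + 0.15 × 1/21 = 1.01.
- Influenza dose on day 45 after the booster: 21 of 48 control days, 1 / (1 + 0.15 × 21/48) = 1/1.0656 = 0.94, for both risk windows.

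An influenza dose on day 21 leaves days 1-21 untouched but raises the IRR for days 22-42 to 1.15. In group II the 1- to 14-day figures hold with the influenza dose on either side of the booster. In Secondary Analysis II they hold only for a booster given before, since a later one ends follow-up.

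Varying r from 1.2 to 2.0, p from 0.1 to 0.5 and the influenza day from −14 to +50, the apparent days 1-21 IRR in group II ranges from 0.82 to 1.48. If p = 0 or r = 1 it is exactly 1.

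**The case against.** The same-day definition is deliberate: the Background describes the observation being followed up as same-day receipt, and the protocol uses that meaning throughout. The explicit list in item II already keeps same-day recombinant and standard-dose recipients out of both groups, so the next sentence may be a drafting slip. The subgroup depends on a feasibility check, Secondary Analysis II is conditional, and the main brand-specific IRRs for the whole population do not use these group definitions. An analysis plan might hold further detail.

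Much of this stands, and it limits the weight of the point. It does not remove it. The conflicting sentences are both current protocol text, and the exclusions and censoring events are set out in the protocol itself. A same-day definition suits group I, but does not make group II free of influenza vaccine.

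A reader might go further in four ways that the protocol does not support:

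- *That both analyses separate the vaccines by same-day receipt only.* The influenza analysis also censors at a later mRNA dose.
- *That an earlier booster puts its whole risk window into the influenza estimate.* Follow-up starts the day after the influenza dose, so only the remainder of the window counts, and the effect fades to 1.01 at 20 days.
- *That the inflation is simply 1 + p(r − 1).* This gives 1.15 for the inputs above, but it is a ceiling that requires complete overlap.
- *That the faulty definition governs whether Secondary Analysis II is run.* Section 5.5.6 triggers it on the concomitant subgroup, group I, whose definition is clear.

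Section 2.1 also still names "those with a prior COVID-19 infection, and those who received a concomitant (same day administration) high-dose or adjuvanted influenza vaccine", although Section 5.5.3 has no prior-infection subgroup. That is a clerical leftover and has no bearing on this point.

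**Conclusion.** The point holds in a limited form. Section 5.5.3.2 contradicts itself on which same-day influenza vaccines exclude a person from group II. Group II has no rule for influenza vaccine on nearby days, and Secondary Analysis II has none for a booster given shortly before.

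Separation of the two vaccines is therefore incomplete. To say that the effects are not separated at all would go too far. The illustrated distortion is modest and can go either way: upward when the doses are close together, downward when an influenza dose falls in control time. Its real size depends on how common off-day receipt is and on the other vaccine's true effect. The protocol gives neither, and either could make the bias nil. The correction should be made because these estimates exist to tell the two vaccines apart and the change is cheap.

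**What to change.** - **Section 5.5.3.2:** use one definition. Group II is booster recipients with no influenza vaccine of any type on the same day or in the preceding 42 days. The 42 days match the protocol's own risk windows and lie within the 365 days of prior enrolment already required. Place same-day recipients of types other than high-dose or adjuvanted in neither group.
- **Section 5.3.2:** exclude anyone with a bivalent dose in the 42 days before the influenza vaccine.
- **Table 6:** tabulate influenza vaccination during days 1-90 after the booster.
- **Sensitivity analysis only:** model influenza doses after the booster as time-varying terms for days 1-21 and 22-42, and state how event-dependent exposure is handled. A stroke can alter later vaccination, which is the first assumption in Section 5.1. For the same reason, do not exclude people because of a later influenza dose. Section 5.1 already cites a method for perturbed post-event exposures, but does not say how it would extend to a second vaccine.

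The look-backs use only history before the index dose. They leave influenza doses after the booster in group II, which is why the table and the sensitivity analysis are needed. The cost is somewhat smaller groups, hence some precision, and extraction of more influenza vaccine codes, since Table 3 lists only the high-dose and adjuvanted products. The time-varying model is more work than the rest.

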#### 5.5.4 Sensitivity Analysis

Adjustments to the primary analysis will be conducted to assess the robustness of the risk estimations from the primary analysis. To evaluate potential time-varying confounding given the length of observation period, the study will assess the association of time-varying risk factors with the stroke outcomes and adjust for the changing risk of the stroke outcomes associated with seasonality. Additionally, to account for potential outcome misclassification, a positive predictive value (PPV) adjusted analysis will be calculated. These analyses will be conducted after the finalization of the primary analyses.

##### 5.5.4.1 Seasonality Adjustment Analysis

To evaluate potential time-varying confounding given the length of the observation period, the study will assess the association of time-varying risk factors with the stroke outcomes and adjust for the changing risk of the stroke outcomes, namely that some of the stroke outcomes exhibit seasonal trends. In addition, given that COVID-19 has been associated with stroke, and the risk of exposure to COVID-19 varies throughout the study period, the risk of related stroke may vary during the study period as well. Baseline stroke outcome risk will be estimated from a similar population during the same calendar months in previous years and will be included as an offset term in the Poisson regression model. For each stroke outcome, rates between 2017-2021 will be evaluated to determine a reasonable comparator year. If rates vary across years, the selected comparator year will be the one with the minimum stroke outcomes rate, whereas if there is limited variation, the median year among 2017-2021 will be selected.

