## 5 Methods

### 5.1 Study Design

The SCCS design compares the incidence of adverse outcomes during periods of hypothesized excess risk due to the exposure (risk interval) to that of the control interval. Only cases (i.e., individuals with an incident stroke outcome) occurring during the study observation period contribute to risk estimation in an SCCS design, with estimation occurring within, rather than between, individuals. However, the SCCS design has a number of assumptions that have to be met in order to ensure valid unbiased risk estimates. These assumptions are outlined below:

- I. Occurrence of an outcome does not substantially affect subsequent exposures
- II. Occurrence of an outcome does not affect the observation length
- III. Outcome rates are constant within risk intervals
  - a. Outcomes must be independently recurrent or rare
  - b. The SCCS method is typically considered valid when the risk of occurrence is 10% or less

Given the fatal nature of some of the stroke outcomes included in the study (discussed below), the occurrence of an outcome can affect both subsequent exposures and reduce the observation length, thus violating both the first and the second assumptions referenced above.

A violation of the first assumption could bias the relative incidence in either direction, thus causing reverse causation bias that would affect subsequent exposures. To address this concern, the primary

analysis will be restricted to a post vaccination control interval which will avoid a bias of reverse causation but require additional data accrual after the post-vaccination risk window.

Given concerns that stroke may have a high mortality rate, we calculated the 30-day Case Fatality Rate (CFR) for each outcome by utilizing SSD data from October 31, 2021-October 31, 2022 for beneficiaries 65 years and older with a 365-day prior clean window relative to the stroke outcomes and Medicare A/B enrollment from 365 days prior to vaccination date. Table 5 displays the case fatality rates within the 30-day observation period after the outcomes.

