## 5.5.2 Primary Analysis: SCCS with Post-vaccination Control Intervals

### 5.5.2.1 Incidence Rate Ratio (IRR) Estimation

For the primary SCCS analysis, the rates of the stroke outcomes following the bivalent booster doses dose will be evaluated by brand. This analysis will compare the stroke outcomes rates in the risk and control intervals using a conditional Poisson regression model. A Farrington-adjusted SCCS model will be implemented that adjusts for the reduced observation time that can occur from the occurrence of an outcome. We assume that only one incident event can occur in the observation period. Therefore, we only consider the first observed outcome.

$$\log(E(Y|X)) = \beta_1(\text{risk window}_1) + \beta_2(\text{risk window}_2) + \log(t) + \text{strata}(\text{pateint id})$$

$Y = \text{Stroke Outcome}$

$\text{risk interval} = \text{indicator for exposure}$

$t = \text{interval}$

$\text{patient id} = \text{term identifying the patient}$

Under this model, the null and alternative hypotheses for each risk window can be written as, respectively:

$$H_0: e^{\beta_1} = 1 \quad H_a: e^{\beta_1} \neq 1$$

$$H_0: e^{\beta_2} = 1 \quad H_a: e^{\beta_2} \neq 1$$

Where,  $e^{\beta_1}$  and  $e^{\beta_2}$  will be interpreted as the IRR for the stroke outcomes in the risk intervals compared to the control intervals. Thus, statistical significance of the coefficient on the risk interval variable at a pre-specified level will indicate a statistically significant association between COVID-19 vaccination and the stroke outcomes. Statistical significance will be determined using 95% CIs of IRRs and two-sided p-values ( $p \leq 0.05$ ).

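### The seasonality offset picks its comparator year by rate level, which cancels in the within-person model, and a 2017-2021 year cannot carry the study-period COVID-19 variation given as a reason for adjusting

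*Protocol*

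**What the plan says.** Protocol Section 5.5.4.1 gives two reasons for the adjustment. Some stroke outcomes are seasonal, and COVID-19 is linked to stroke while "the risk of exposure to COVID-19 varies throughout the study period, the risk of related stroke may vary during the study period as well".

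The one mechanism it specifies is a baseline risk "estimated from a similar population during the same calendar months in previous years and will be included as an offset term". The year is chosen as follows: "For each stroke outcome, rates between 2017-2021 will be evaluated to determine a reasonable comparator year". The first branch of the rule is: "If rates vary across years, the selected comparator year will be the one with the minimum stroke outcomes rate". The second branch, for years that differ little, is: "whereas if there is limited variation, the median year among 2017-2021 will be selected". No criterion concerns the pattern over months, and no term uses COVID-19 incidence from the study period.

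The offset enters the model of Section 5.5.2.1: "This analysis will compare the stroke outcomes rates in the risk and control intervals using a conditional Poisson regression model", stratified on patient. Section 5.1 describes the design as one "with estimation occurring within, rather than between, individuals".

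Three other places bear on the point:
- Section 5.2 starts the study on August 31, 2022.
- Sections 5.4.2 and 5.4.3 set risk windows at days 1-21 and 22-42 and use the remaining follow-up, to day 90 at most, as control time.
- Section 5.3.1 and Appendix Table A exclude cases with COVID-19 in the 30 days before the stroke.

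**The concern.** All control time is post-vaccination, so in every person days 43-90 fall later in the calendar than days 1-42. No pre-vaccination control time balances a rising or falling baseline. A trend in stroke risk over the autumn and winter therefore goes directly into the IRR unless the offset has the right shape.

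The rule selects on a feature that has no effect in this model. Whichever year it picks brings a seasonal shape that nobody chose, and the choice is made separately for each outcome. Taking the lowest year may look cautious, but here it pushes the IRR in no particular direction.

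The second part is chronological. An offset from 2017-2021 cannot contain COVID-19 variation that occurred from August 31, 2022 onward. At stake is how the result is read: an adjusted IRR close to the primary one could be reported as robustness to season and COVID-19 when the offset had the wrong shape for the first and no information on the second.

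**Working it through.** The protocol states no figure for this adjustment, so there is none to reproduce.

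**Step 1: level cancels.** Let t_j be the length of window j, b_j the baseline in the offset and β_j the log IRR (zero for control time). Given one event per person,

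P(event in window j) = t_j·b_j·exp(β_j) / Σ_k t_k·b_k·exp(β_k).

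Replacing b by c·b multiplies numerator and denominator by c, so c disappears. The result is exact and needs no assumed numbers.

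**Step 2: numerical check.** A simulated SCCS had 400,000 cases, windows 1-21, 22-42 and 43-90, and a true IRR of 1. Assumed, not from the protocol: seasonal amplitude 8%, mid-January peak, and vaccination dates centred 45 days after August 31 with SD 20 days. Death and the Farrington adjustment were not simulated.

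| Offset used | IRR days 1-21 | IRR days 22-42 |
|---|---|---|
| Correct shape, level ×0.5, 0.8, 1, 1.25 or 2 | 0.997 each time | 1.005 each time |
| Flat | 0.947 | 0.979 |
| Peak 60 days too early | 0.939 | 0.966 |
| Double amplitude | 1.047 | 1.031 |

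A fourfold range of level changes nothing. At equal level, shape alone moves the days 1-21 IRR from 0.939 to 1.047.

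**Step 3: size of a missed trend.** Take full follow-up, so t = 21, 21, 48, with no vaccine effect. Let the control-period baseline be (1 + x) times the risk-period baseline, with an offset that treats them as equal. The estimate for days 1-21 is

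[21 / (48·(1 + x))] / [21 / 48] = 1 / (1 + x).

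- x = 2%: 1/1.02 = 0.980
- x = 5%: 1/1.05 = 0.952
- x = 10%: 1/1.10 = 0.909

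A baseline that falls into the control period gives the opposite error. The x values are assumptions; the protocol gives no monthly rates.

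**Step 4: scale.** The protocol gives no case counts. With an assumed 5,000 cases spread evenly over 90 days, days 1-21 hold 5,000·21/90 = 1,167 and days 43-90 hold 5,000·48/90 = 2,667. The SE of the days 1-21 log IRR is sqrt(1/1167 + 1/2667) = 0.035. A missed 5% trend shifts the log IRR by ln(1.05) = 0.049, more than one SE. A missed 2% trend shifts it by 0.020, less than one SE. Case counts will differ by outcome and brand.

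**Step 5: cost of calendar-time terms.** The conditional-likelihood information was computed under the null, again for 5,000 cases, for three assumed spreads of vaccination dates (uniform over 120 days, a skewed autumn peak, and a narrow 47 days). The SE of the days 1-21 log IRR rises from 0.035 to 0.079-0.086 with 2-week terms and to 0.070-0.075 with 4-week terms, about double or a little more.

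**The case against.** The strongest reply is that this is a sensitivity analysis run after the primary analysis is final, and that the COVID-19 part is already handled: cases diagnosed in the 30 days before the stroke are excluded. Sections 5.5.4 and 5.5.4.1 also promise to assess time-varying risk factors, and Section 8 plans negative-control checks. Much of this stands. The exclusion removes strokes after recently diagnosed infection, which leaves undiagnosed infection and later effects. However, the promised assessment names no COVID-19 term, the Section 8 checks are for data quality, and none of this repairs the year-selection rule.

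Some stronger readings are tempting but not supported:

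- *The choice of year makes no difference.* It does, because it fixes whose shape is used. The fault is that the criterion does not target shape.
- *The rule will pick a pandemic year with distorted hospital care.* The protocol gives no yearly rates, so this is conjecture.
- *A particular 2022-23 wave biases the result by a known amount.* The protocol says only that exposure risk varies. In the simulation, assumed waves of 5% to 30% missing from the offset gave days 1-21 IRRs of 0.969 down to 0.861. Those runs ignore the 30-day exclusion and probably overstate the residual.
- *Calendar-time terms are a nearly free remedy.* Within a person, calendar time is a constant plus time since vaccination. Staggered vaccination dates alone cannot separate a linear calendar trend from a linear effect of time since vaccination. Constant risk within each window must also be assumed, and precision falls as in Step 5. Section 5.4.2 already declines to split the risk windows further in order to keep power.

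**Conclusion.** The point holds for the year-selection rule and for the COVID-19 rationale. The cancellation is exact for the patient-stratified conditional Poisson model as written, and the chronological gap follows from the protocol's own dates. This is a rule fixed wrongly, not a detail left to a later plan.

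The size is conditional. The error is 1/(1 + x) for whatever control-to-risk trend the offset misses: 0.98 to 0.91 over an assumed 2% to 10%. The direction depends on whether the baseline rises or falls between risk and control time, which the protocol does not show.

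A reader might infer that the primary IRR is wrong because of this rule. It is not; the offset enters only the sensitivity analysis. What is weakened is the only specified sensitivity analysis aimed at calendar trend, and so the assurance that can be drawn from it.

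**What to change.** 1. In Section 5.5.4.1, replace the minimum-or-median rule. For each outcome, compute the seasonal profile within each historical season, normalise it to its own mean, average over several years, and use that average as the offset. Show the IRR with each individual year's profile too, so that dependence on shape is visible.
2. For COVID-19, do one of two things. Either build the offset from contemporaneous study-period rates, or state that the historical offset does not adjust for study-period COVID-19 and that only the 30-day exclusion addresses it.
3. Calendar-time terms of 2 or 4 weeks may be added as a supplementary check. State that they rely on constant risk within each window and roughly double the SE of the days 1-21 log IRR (about 0.035 to 0.070-0.086 at an assumed 5,000 cases).

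The first two changes cost a little more analysis work on data already held and leave the primary analysis as it is. The third costs precision, so it should not be the main adjustment.
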